#### Table 1-2 The PASI scoring system

\* Percentage (not score) of body region (not whole body) affected will be entered in the eCRF

+ Neck is assessed as part of the Head (H) body region.

‡ Axillae and groin are assessed as part of the Trunk (T) body region.

§ Buttocks are assessed as part of the Lower limbs (L) body region.

The following definitions are possible efficacy evaluations that can be used in clinical trials in psoriasis (CHMP/EWP/2454/02, 2004):

- **PASI non response:** subjects achieving <50% improvement (reduction) in PASI score compared to baseline are defined as PASI non responders
- **Partial response**: subjects achieving ≥ 50% improvement (reduction) in PASI score but less than 75% compared to baseline are defined as partial responders
- **PASI 50 response**: subjects achieving ≥ 50% improvement (reduction) in PASI score compared to baseline are defined as PASI 50 responders
- **PASI 75 response**: subjects achieving ≥ 75% improvement (reduction) in PASI score compared to baseline are defined as PASI 75 responders

Novartis	Confidential	Page 32
RAP Module 3	9-Apr-2018 (1:15)	Secukinumab / AIN457A2302E1

- **PASI 90 response**: subjects achieving ≥ 90% improvement (reduction) in PASI score compared to baseline are defined as PASI 90 responders
- **PASI 100 response**: complete clearing of psoriasis (PASI=0)
- **Relapse**: when the achieved maximal PASI improvement from baseline PASI in core is reduced by >50%
- **Rebound-like event**: defined as increase of PASI of more than 25% from baseline value or occurrence of new pustular, new erythrodermic or more inflammatory psoriasis **after** stopping therapy
- Rebound: defined as rebound like event occurring within 8 weeks of stopping therapy

The analysis of rebound will be done for the follow-up period.

The number and percentage of subjects experiencing rebound and rebound like events will be presented by treatment group as follows:

- For rebound, all assessments done up to 8 weeks will be summarized.
- Similarly for rebound like events, all assessments done up to 12weeks will be summarized.
  - 1. Rebound up to 8 weeks: For this time-point the worst outcome (i.e. rebound like event=yes) prior to this cut-off is considered (e.g. if a subject had >25% PASI increase at Week 260, but not at Week 264 the subject would be considered as rebounder for this "up to 8 week timepoint").
- Rebound like events up to 12 weeks: For this time-point the worst outcome (i.e. rebound like event=yes) prior to this cut-off is considered.

## Definition of IGA mod 2011 score and IGA mod 2011 0 or 1 response

The IGA mod 2011 rating scale for overall psoriatic disease (shown in Table 1-11) has been developed based on a previous version of the scale used in secukinumab phase II studies, and has been updated in collaboration with health authorities (in particular the FDA.).The explanations/descriptions of the points on the scale have been improved to ensure appropriate differentiation between the points.

The IGA mod 2011 used in this study is static, i.e., it refers exclusively to the subject's disease state at the time of the assessments, and does not attempt a comparison with any of the subject's previous disease states, whether at baseline or at a previous visit.

Score	Short Description	Detailed Description
0	Clear	No signs of psoriasis. Post-inflammatory hyperpigmentation may be present.
1	Almost clear	Normal to pink coloration of lesions; no thickening; no to minimal focal scaling.
2	Mild	Pink to light red coloration; just detectable to mild thickening; predominantly fine scaling.
3	Moderate	Dull bright red, clearly distinguishable erythema; clearly distinguishable to moderate thickening; moderate scaling.
4	Severe	Bright to deep dark red coloration; severe thickening with hard edges; severe / coarse scaling covering almost all or all lesions.

Table 1-3 The IGA mod 2011 rating sca	Table 1-3	The IGA mod 2011 rating scale	
---------------------------------------	-----------	-------------------------------	--

Note: Involvement of nails is not part of the assessment.

Based on this scale, subjects will be considered as **IGA mod 2011 0 or 1 responder** if they achieve a score of 0 or 1 and improve by at least 2 points on the IGA scale compared to baseline.

#### 1.9.1.2 Health Assessment Questionnaire - Disability Index (HAQ-DI)

The Health Assessment Questionnaire (HAQ©) was developed by Stanford University and is one of the most widely used measures to assess the long-term influence of chronic disease on a subject's level of functional ability and activity restriction. The disability assessment component of the HAQ (Health Assessment Questionnaire – Disability Index), the HAQ-DI, assesses a subject's level of functional ability and includes questions of fine movements of the upper extremity, locomotor activities of the lower extremity, and activities that involve both upper and lower extremities. There are 20 questions in eight categories of functioning including dressing, rising, eating, walking, hygiene, reach, grip, and usual activities. The stem of each item asks over the past week "Are you able to ..." perform a particular task. Each item is scored on a 4-point scale from 0 to 3, representing normal (normal, no difficulty [0]), some difficulty [1], much difficulty [2], and unable to do [3].

Scoring for the eight functional categories and overall disability index scoring will be performed as follows:

There are eight categories; first score within each category:

- Dressing and Grooming, includes items 1 and 2
- Arising, includes items 3 and 4
- Eating, includes items 5, 6 and 7
- Walking, includes items 8 and 9
- Hygiene, includes items 10, 11, and 12
- Reach, includes items 13 and 14
- Grip, includes items 15, 16 and 17
- Activities, includes items 18, 19, and 20

Novartis	Confidential	Page 34
RAP Module 3	9-Apr-2018 (1:15)	Secukinumab / AIN457A2302E1

The score for each category will be the single response within the category with the highest score (greatest difficulty). For example, in the "Eating" category, there are two answers (one for each item). If "Cut your food with a knife or fork" is marked as "3" and "Lift a full cup or glass to your mouth" is marked as "0", then the score for the "Eating" category would be "3" (the response indicating the greatest difficulty within the category). If a component question is left blank or the response is too ambiguous to assign a score, then the score that that category will be determined by the remaining completed question(s). However, if any "aids or devices" and/or "help from another person" items at the bottom of each page are checked with the exception of "other", the category to which they apply will be adjusted upward to "2". If the basic score is already "2" or "3", the score remains unchanged. "Aids or devices" and "help from another person" can only change a category's score to "2"; they do not change the score to a "1" or a "3". Companion aids/devices items for HAQ-DI categories are presented in Table 1-12. No score will be adjusted for "other" ticked, regardless of the "other" specification.

The score for the disability index will be the mean of the eight category scores. If more than two of the categories, or 25%, are missing, scale will not be scored. If fewer than 2 of the categories are missing, divide the sum of the categories by the number of answered categories. The higher score indicates greater disability.

HAQ-DI response is defined by an improvement of at least 0.3 score points compared to baseline.

HAQ-DI Category	Companion Item
Dressing & Grooming	Devices used for dressing (button hook, zipper pull, long handled shoe horn etc.)
Arising	Built up or special chair
Eating	Built up or special utensils
Walking	Cane walker, crutches
Hygiene	Raised toilet seat, bathtub seat, bathtub bar
	Long handled appliances in bathroom
Reach	Long handled appliances for reach
Grip	Jar opener (for jars previously opened)

 Table 1-4
 Companion aids/devices items for HAQ-DI categories

#### 1.9.1.3 Overview of analysis methods of efficacy variables

An overview of statistical analyses and methods applied to psoriasis efficacy variables is given in Table 1-13.

#### Table 1-5 Overview of analysis methods for efficacy variables

Variable(s)	Summary statistics for binary/ categorical data	Cochran- Mantel- Haenszel test	Logistic regression	Summary statistics for continuous data	Time-to- event data analysis	Graphs
PASI 50/75/90/100 over time	Х	Х	Х			X 
Loss of PASI 75 response over time during RW period	Х				Х	
Loss of IGA 0 or 1 response over time during RW period	Х				X	
Absolute PASI score over time				х		
% change PASI over time				Х		
IGA mod 2011 0 or 1 response over time	Х	Х	Х			
IGA mod 2011 score over time by categories				Х		
Relapse	Х				Х	Х
Rebound	Х					
EQ-5D	Х			х		
Absolute DLQI 				х		
% change DLQI 				Х		
DLQI 0 or 1 achievement	Х					
HAQ-DI score over time				X 		
HAQ-DI response over time	X 	T				

only for subjects who were PASI 75 responders at Week 52

only for subjects with psoriatic arthritis at baseline

additional analyses for subjects who were PASI 75 responders at Week 52 described below

#### 1.9.2 Statistical hypothesis, model, and method of analysis

The statistical hypotheses are that the cumulative rate for subjects who lost PASI 75 response up to Week 68 are not different between secukinumab 150 mg and corresponding placebo as well as between secukinumab 300 mg and corresponding placebo.

Loss of PASI 75 response will be analyzed by means of a survival analysis defining "loss of PASI 75 response" as "failure". The term *cumulative rate* corresponds to 1 minus the survival function within this survival analysis, and the cumulative rate as well as the survival functions are dependent on time *t*.

Hence, the null hypothesis for each dose corresponds to the usual null hypothesis within a survival analysis: The survival functions of the two groups are not different and will be tested versus the alternative, that the survival functions are different.

If the survival functions are different, they must be different at at least one time point within the analysis period. The analysis period in the primary analysis is Week 52 to Week 68.

Let pj(t) denote the proportion of PASI 75 responders at time *t* for treatment group *j*, and let p0,j(t) denote the proportion of PASI 75 responders at time *t* for placebo group *j*, *j*=1, 2, where

- 0,j corresponds to placebo (secukinumab 150 mg in core studies) for j=1 and to placebo (secukinumab 300 mg in core studies) for j=2,
- 1 corresponds to secukinumab 150 mg,
- 2 corresponds to secukinumab 300 mg.

The following hypotheses will be tested for 52 weeks $\leq$  t  $\leq$ 68 weeks

- $H_1: p_1(t) p_{0,1}(t) = 0$  for all t, 52 weeks  $\le t \le 68$  weeks, versus  $H_{A1}:$  there is at least one t with  $p_1(t) p_{0,1}(t) \ge 0$ ,
- $H_2: p_2(t) p_{0,2}(t) = 0$  for all t, 52 weeks  $\le t \le 68$  weeks, versus  $H_{A2}:$  there is at least one t with  $p_2(t) p_{0,2}(t) \ge 0$ ,

In other words

- H1: Secukinumab 150 mg is not different from placebo with respect to the cumulative rate for subjects who lost PASI 75 response up to Week 68
- H2: Secukinumab 300 mg is not different from placebo with respect to the cumulative rate for subjects who lost PASI 75 response up to Week 68

The primary analysis will not be conducted in the final analysis, instead loss of PASI 75 response during RW will be tested.

Number and percentage of subjects with loss of PASI 75 response based on the number of subjects in the full analysis set at risk as denominator will be provided by treatment group.

For loss of PASI 75 response, between-treatment differences will be evaluated using a logrank test, stratified by geographical region and body weight stratum, to compare the survival functions between secukinumab treatment groups versus placebo. The hazard ratios for these comparisons for loss of PASI 75 response and their corresponding 95% confidence intervals will be computed using a stratified Cox proportional hazards regression model with treatment group, core study and baseline PASI of core study and baseline PASI of extension study as explanatory variable and stratified by geographical region and body weight stratum.

Kaplan-Meier estimates including 95% confidence intervals for cumulative rate of subjects losing PASI 75 response will be calculated for each treatment group.

The number of subjects with loss of PASI 75 response, number of subjects in the analysis set, estimate of cumulative rate during RW period, median event time, and its estimated standard

Novartis	Confidential	Page 37
RAP Module 3	9-Apr-2018 (1:15)	Secukinumab / AIN457A2302E1

error, as estimable will be provided for each treatment group. In addition, for pre-specified time intervals (e.g., 4-week intervals) the following will be presented:

[figure not shown]
- for each treatment group and time interval: subjects at risk, subjects with loss of PASI 75 response, subjects with loss of PASI 75 response divided by subjects at risk, cumulative subjects with event and cumulative event probability including 95% confidence interval.
- for treatment comparisons the log-rank test and Wilcoxon test as well as the hazard ratio derived via Cox regression.

## 1.9.3 Testing strategy

The family wise error will be set to  $\alpha$ =2.5% (one-sided). The two hypotheses H1 (referring to 150 mg) and H2 (referring to 300 mg) will be tested at  $\alpha$ /2=1.25% one-sided. In case, a null hypothesis has been rejected for one dose, but not for the other dose, the alpha can be shifted to the other dose and the null hypotheses can be retested at level  $\alpha$ =2.5% (one-sided).

The graphical approach of Bretz et al. 2009 for sequentially rejective testing procedures is used to illustrate the testing strategy:

## Figure 1-1 Testing strategy

Note - Other secondary endpoints will not be included in the testing strategy.

## 1.9.4 Handling of missing values/censoring/discontinuations

#### For the analyses re-run during RW period

The loss of PASI 75 response during RW period will be re-run. The subjects who have no lost PASI 75 response during RW will be considered as censored observations. Subjects who have not lost PASI 75 response but with missing values during RW will be considered as censored at prior available visit. Subjects who administered psoriasis concomitant medication (as per [MAP Appendix]), will be considered as failures at time of first administration if this occurred before the loss of PASI 75. Subjects who did not have PASI 75 response but randomized in RW period will be censored at day 0. Subjects with missing values at week X (X <156) and who have not lost PASI 75 response earlier, will be censored at week X (if they have not dropped out due to lack of efficacy or not administered psoriasis concomitant medication). Subjects who drop-out due to lack of efficacy will be considered as failure at time of drop-out. If drop-out was due to other reason, subjects will be considered as censored at time of drop-out. Intermediate missing values will not be considered.

Other time-to-event analyses will be handled analogously. For imputation techniques, please refer to Table 1-16.

For other analyses (not time to event) missing values with respect to response variables based on PASI score and IGA mod 2011 score will be imputed with multiple imputation regardless of the reason for missing data (e.g., premature study discontinuation, missed visit, administrative issues).

Following the intent-to-treat principle for subjects who prematurely discontinue treatment, but who are observed in the follow-up period, efficacy data collected in follow-up periods will be linked to planned but missed study visits as well, following imputation schemes described in Sections 1.5.4.1 and 1.9.4.2. (e.g., if a subject discontinues treatment at Week 56, but has follow-up visit F4, the PASI score observed at Visit F4 might be used for Week 60 assessments).

Novartis	Confidential	Page 39
RAP Module 3	9-Apr-2018 (1:15)	Secukinumab / AIN457A2302E1

For rebound and relapse no imputed data will be used and analyses will be based on observed data only.

The last observation carried forward method (LOCF) will be applied to PASI score and IGA mod 2011 score that are missing after baseline regardless to the reason for missing data (e.g. premature study discontinuation, missed visit, administrative issues). Note that LOCF imputations will not be considered for response variables based on PASI score or IGA score which will be imputed with non-response, see above. Baseline values will not be carried forward.

If all post Randomization Visit efficacy values are missing for one efficacy parameter then these missing values will not be imputed and this subject will be removed from the analysis of the corresponding variable, *i.e.*, it might be that the number of subjects providing data to an analysis is smaller than the number of subjects in the FAS. In addition, missing baseline values will not be imputed.

For subjects who were re-treated after relapse with secukinumab 150 mg or secukinumab 300 mg amongst PASI 75 responders at week 52, values of RW period are not carried forward to treatment period.

For HAQ score and derived variables, EQ-5D and DLQI missing values will be replaced by LOCF. Missing responses will also be imputed by LOCF. Baseline values will not be carried forward.

The laboratory values below Lower Level Of Quantification (LLQ) or above Upper Level of Quantification (ULQ) will be imputed as LLQ or ULQ, respectively. The numerical part of the reported result will be treated as the actual LLQ or ULQ. These laboratory values will be displayed in listings using the standard unit with the reported sign ("<" or ">")."

## For the final analysis

For subjects who prematurely discontinue treatment, but are observed in the follow-up period, efficacy data collected in follow-up periods will not be linked to planned study visits.

The following missing data imputation methods will apply to PASI and IGA score or response variables in the final analysis:

- Response variables based on PASI score and IGA mod 2011 categories will be generally be presented as 'observed case'; i.e. all available data for each time point will be included in the analyses.
- For subjects who received secukinumab dose from week 52, multiple imputation will be used as the sensitivity method

Novartis	Confidential	Page 40
RAP Module 3	9-Apr-2018 (1:15)	Secukinumab / AIN457A2302E1

# 1.9.4.1 Details for imputations (non- responder and LOCF) and visit windowing

Note: These details are not applicable to time to event analysis. Only PASI and IGA mod 2011 based response variables are imputed with non-response, other response variables (e.g. for HAQ-DI, EQ-5D, DLQI) will be imputed with LOCF. Baseline values will not be carried forward. If all post baseline values are missing for one efficacy parameter, then these missing values will not be imputed and this subject will be removed from the analysis of the corresponding variable.

- Non- responder imputation for subjects with PASI 75 response at Week 52 RW period (Week 52 up to Week 156)
  - 1. Assign period to each visit as per CRF visit (CRF period) or as per visit date for unscheduled visits (analysis period)
  - 2. Assign analysis visit windows (for RW period from week 52 up to Week 156) according to Section 1.5.4. Of note, RW CRF period visits will not be assigned to treatment analysis period, whereas follow-up period CRF visits might be assigned to RW analysis period for subjects who do not enter treatment CRF period)
  - 3. If no CRF visit is assigned to an analysis visit as per Section 1.5.4, impute non-response

Note – Subjects with PASI 75 response at week 52 enter RW period. RW period is not fixed for all the subjects but varies for subject to subject based on occurrence of relapse. Subjects in RW period will enter treatment period only after first full relapse, if it occurs; otherwise not. Partial responders are not entering the RW period but go into the treatment period.

- LOCF imputation
- 1. Assign period to each visit as per CRF visit (CRF period) or as per visit date for unscheduled visits (analysis period)
- 2. Assign analysis visit windows (for RW period from week 52 up to Week 156) according to Section 1.5.4. Of note, RW CRF period visits will not be assigned to treatment analysis period, whereas follow-up CRF period visits might be assigned to RW analysis period for subjects who do not enter treatment CRF period)
- 3. If no CRF visit is assigned to an analysis visit as per Section 1.5.4, impute with LOCF

Note: All data collected in the eCRF will be considered for LOCF imputation regardless of whether the data was considered in analysis visit windows.

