Week 132	132	561	Day 548-575
Week 136	136	589	Day 576-603
Week 140	140	617	Day 604-631
Week 144	144	645	Day 632-659
Week 148	148	673	Day 660-687
Week 152	152	701	Day 688-715
Week 156	156	729	Day 716-743
Week 168	168	813	Day 744-855
Week 180	180	897	Day 856-939
Week 192	192	981	Day 940-1023
Week 208	208	1093	Day 1024-1149
Week 220	220	1177	Day 1150-1219
Week 232	232	1261	Day 1220-1303
Week 244	244	1345	Day 1304-1387
Week 260	260	1457	Day 1388-1471
Week 264	264	1485	Day 1472-1499
Week 268	268	1513	Day 1500-1527
3 WK after last study drug admin.**			Week 264 visit

Novartis	Confidential	Page 21
RAP Module 3	9-Apr-2018 (1:15)	Secukinumab / AIN457A2302E1

12 WK after last study		Week 268 visit
drug admin.**		

\* Baseline measurement before the first drug administration for safety assessments and before the randomization for efficacy assessments. The days are counted since the first dose of study treatment in extension for safety assessments, and the days are counted since the date of randomization in extension for efficacy assessments.

\*\* 8/12 WK after last study drug administration will be used for re-bound analysis.

For parameters which are not collected at every visit (e.g. DLQI, EQ-5D, HAQ-DI), visit windows defined in Table 1-5 will be combined. For example, if a parameter is measured at Week 64 and Week 76 only, Week 64 visit window will extend from Day 2 to Day 99 (combining Week 56 to Week 64 visit windows), Week 76 will extend from Day 100 to Day 183 (combining Week 68 to Week 76). If more than one assessment falls into the interval, the rules defined in section 1.5.5 below are applied.

Assessments from treatment period will not be considered for RW period. Assessments from RW period will not be considered for treatment period. Assessments from RW and treatment period may be considered for follow-up period.

Assessments from RW/treatment period will not be considered for open label period. Assessments from open label period will not be considered for RW/treatment period.

The 'by visit' safety summaries for the 'whole treatment period' will be reported as per the analysis visits relative to Week 52 as defined in Table 1-5.

Of note, for subjects who discontinue in RW period, i.e. not moving into treatment period, efficacy measurements taken in follow-up period would still be considered for RW period as specified in Section 1.9.4.1.

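### The re-run DLQI analysis for the randomised-withdrawal period has no rule for relapse, and the SAP's general missing-data rules can favour placebo

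*SAP*

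**What the plan says.** SAP 1.1 and Tables 1-4 and 1-9 list DLQI and DLQI 0/1 among the analyses re-run for RW. The rules that govern them are spread over several sections.

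- SAP 1.9.4, on the RW re-run: "For HAQ score and derived variables, EQ-5D and DLQI missing values will be replaced by LOCF". SAP 1.9.4.1 repeats that "other response variables (e.g. for HAQ-DI, EQ-5D, DLQI) will be imputed with LOCF". Baseline is not carried.
- SAP 1.9.4.1, LOCF steps, with RW windows running to Week 156: "If no CRF visit is assigned to an analysis visit as per Section 1.5.4, impute with LOCF".
- SAP 1.5.4: "Assessments from treatment period will not be considered for RW period". The same section names DLQI among the measures not taken at every visit and combines their windows.
- SAP 1.9.4.1: "If all post baseline values are missing for one efficacy parameter, then these missing values will not be imputed and this subject will be removed".

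Other text points elsewhere. SAP 1.3 ends RW at first full relapse, and at Week 156 only without one. SAP 1.9.6 stops the RW comparisons of PASI and IGA response with placebo once 5% or fewer of placebo subjects remain. SAP 1.9.4 does not allow RW values to pass into the treatment period. The closing note of 1.9.4.1 says "All data collected in the eCRF will be considered for LOCF imputation regardless of whether the data was considered in analysis visit windows".

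**The concern.** DLQI against placebo in Week 52 PASI 75 responders is a named secondary objective (protocol 2.2). In this design relapse is an outcome of withdrawal, and it also moves the subject out of RW and on to re-treatment. An analysis by visit up to Week 156 therefore has to say what a relapsed subject contributes afterwards. The SAP does not say so for DLQI; the general missing-data rules decide it by default. Because relapse should be concentrated on placebo, any default that hides its effect on quality of life acts mainly on one arm.

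**Working it through.** The documents give no DLQI figure to reproduce. Their only figure for full relapse after withdrawal is a model prediction of 10% at four months (protocol 3.3). Everything else numeric below is an assumption.

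**1. The rules side by side**

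| Reading | Text behind it | What represents a relapser at later RW visits |
|---|---|---|
| A. Fill empty windows | 1.9.4, LOCF steps of 1.9.4.1, 1.5.4 | Last DLQI before re-treatment |
| B. Leave RW at relapse | 1.3, 5% rule in 1.9.6 | Nothing; only non-relapsers remain |
| C. Any eCRF value may be carried | Closing note of 1.9.4.1 | Possibly a DLQI taken on re-treatment |

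The bar in 1.9.4 on passing RW values into the treatment period does not decide between A and B. It can be read as covering only the treatment-period analysis.

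**2. Who is removed under A**

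Relapse visits R1 to R3 list no DLQI (protocol Table 6-1, footnote 11). The DLQI row of Table 6-1 for Weeks 52 to 156 is not legible in the copy used here, which is not a fault of the plan. Assume Weeks 64, 76, 88, 104, 116, 128, 140 and 156, the visits at which protocol Table 13-1 requires PK samples from everyone. A relapse found at Week 56 or 60 then leaves no RW DLQI. With a constant hazard to Week 68:

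- placebo, 10% relapse by Week 68: 1 − 0.90^(8/16) = 5.1%, about 7 of 138
- placebo, 20%: 1 − 0.80^(8/16) = 10.6%, about 15 of 138
- secukinumab, assumed 2%: 1 − 0.98^(8/16) = 1.0%

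If DLQI were taken at every visit, nobody would be removed.

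**3. DLQI 0/1 on placebo at Week 156**

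Assume 60% relapse by Week 156 at constant hazard, 70% DLQI 0/1 under control and 10% at a relapse visit. Of 26 post-baseline visits, 18 have no DLQI on the assumed grid. Shares of the arm:

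- relapse at Week 56 or 60, removed: 1 − 0.40^(8/104) = 6.8%
- relapse at a DLQI visit: 18.0%
- relapse at a later visit without DLQI: 35.2%
- no relapse: 40.0%

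Let q be the DLQI 0/1 rate at the last DLQI before relapse, for relapses that fall between DLQI visits.

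LOCF rate = (0.40 × 0.70 + 0.180 × 0.10 + 0.352 × q) / (1 − 0.068)

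- q = 0.70 (skin still fully controlled): 0.544 / 0.932 = 58%
- q = 0.25 (disease worsening): 0.386 / 0.932 = 41%
- q = 0.10: 0.333 / 0.932 = 36%

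Relapse counted as not achieved, all subjects in the denominator: 0.40 × 0.70 = 28%. Under reading B the same inputs give 70%, in the 40% of the arm still in RW.

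With 40% to 80% relapse, 50% to 70% control and q equal to the control rate, LOCF gives 39% to 62% against 10% to 42%.

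**4. Direction of the score contrast (placebo minus secukinumab) at Week 156**

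A simulation assumed DLQI 2 in response, rising over 12 weeks to 10 at relapse and staying there if untreated; 3 after re-treatment of placebo relapsers; 7 after relapse on secukinumab; relapse by Week 156 of 50% to 90% on placebo and 15% on secukinumab.

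| Quantity | Contrast |
|---|---|
| Relapsers never re-treated | 2.79 to 6.00 |
| LOCF, assumed 12- to 16-weekly DLQI grid | 1.68 to 3.82 |
| Only subjects still in RW | 0.16 to 0.70 |
| Actual values after re-treatment | −0.17 to 0.21 |

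On the assumed grid, LOCF falls short of the never-re-treated contrast but exceeds the contrast in actual values. With 4-weekly DLQI it equals the never-re-treated contrast, partly because DLQI was assumed flat after relapse.

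**The case against.** A reader might infer more: that pre-relapse values are certainly carried to Week 156, that the contrast is biased toward no effect, and that 58% against 28% measures the error. The documents do not support that, for these reasons.

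- Carry-forward to Week 156 is one reading of three.
- The direction depends on the target. Against actual values after re-treatment, LOCF at Week 156 exaggerates the contrast.
- The last DLQI before relapse need not reflect controlled skin. Protocol 3.3 predicts loss of PASI 75 at about 10% a month but full relapse in only 10% after four months, so many relapsers will already have worsened. A DLQI taken at the relapse visit itself precedes re-treatment and reflects relapse.
- It is tempting to say that one subject will be a PASI 75 failure and a DLQI 0/1 achiever at the same visit. That needs the non-response rule in 1.9.4.1, whereas another paragraph of 1.9.4 assigns multiple imputation to the same PASI and IGA responses.
- The efficacy methods overview (Table 1-13) promises, in a footnote, "additional analyses for subjects who were PASI 75 responders at Week 52 described below", and SAP 1.9.10 gives only summaries. That is mostly missing detail: SAP 1 and 1.1 defer to protocol Section 9, which contains the Van Elteren and Fisher comparisons, and SAP 1.1.1 does not withdraw them.
- Counting relapse as failure is a choice of estimand and makes DLQI partly restate relapse.

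All of this limits the claim about size and direction. It does not supply the missing rule. Readings A and B, which use RW data only, can both favour placebo against the course without re-treatment. Reading C can too, if re-treatment improves DLQI. Actual values after re-treatment are not the RW question either, since 1.5.4 excludes them and re-treated subjects are analysed as a separate group.

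**Conclusion.** The concern stands as a gap with a likely but unquantified lean. The SAP does not say which DLQI values count after relapse in RW, its passages conflict, and its literal rules can exclude early relapsers because of their outcome. Those subjects have post-baseline PASI and so qualify for the full analysis set on that criterion; only the removal rule for each variable takes them out.

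Placebo can be flattered relative to the course without re-treatment. No single figure should be claimed: the 36% to 58% against 28%, and the 5% to 11% of placebo removed, rest on an assumed DLQI schedule, relapse rate and DLQI level. A firm statement of bias toward no effect is not supported.

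Confidence is moderate. SAP 1.9.3 keeps secondary endpoints out of the testing strategy, so the primary conclusion is untouched. The change should be made but is not critical.

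**What to change.** In SAP 1.9.4 and 1.9.4.1:

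1. Reconcile the RW definition in 1.3, the exclusion in 1.5.4, the two imputation rules for PASI and IGA responses in 1.9.4 and 1.9.4.1, the closing note of 1.9.4.1 and the 5% rule in 1.9.6. State the target of the RW DLQI comparison.
2. For RW DLQI 0/1, count every visit after first full relapse, or after exit for lack of efficacy, as not achieved, in line with the PASI/IGA non-response rule in 1.9.4.1. Keep all randomised relapsers in the denominator, including those with no RW DLQI.
3. Do not carry DLQI scores past relapse, and say how relapse enters the score comparison. Refer explicitly to the protocol 9.5.3 tests, or describe them in 1.9.10.
4. Keep LOCF as a sensitivity analysis.
5. Label the change as made after the sponsor was unblinded at the Week 68 analysis (protocol 5.4 and 9.6), since it lowers mainly the placebo results.

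The cost is SAP wording and one derivation rule, with no new data. DLQI 0/1 will also fall somewhat for secukinumab relapsers, and the endpoint will partly reflect relapse.
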